11.2 Final Analysis Plan

Analysis plan for Primary Objectives:

#1. To characterize methods of diagnosing DH in the practice setting.

(This will done by asking questions by means of an online questionnaire on what practitioners usually do when diagnosing DH.)

Practitioners' responses to questionnaire items will be summarized and reported as frequencies and percentages. Ninety five percent confidence intervals will be calculated for percentages. The primary analytic approach for this Aim will not be based on hypothesis testing.

#2. To characterize dentists' selected treatment(s) of DH.

Analysis approach: This descriptive aim will be addressed by tabulating the treatment modalities used by practitioners during the study. Percentages of practitioners using each modality and percentages of total patients who received each modality will be calculated. Confidence intervals for percentages of patients receiving each of the treatment modalities will be calculated, with adjustment for clustering by dentist. Comparisons of percentages among the treatment modalities will be conducted using a mixed model logistic regression, to account for the effect of correlation due to obtaining multiple observations from each practitioner. A term representing the individual practitioner will be specified as a random effect in the analytic model, and estimation will be implemented using GEE. An indicator variable representing treatment modality will be included as a fixed effect.

#3. To characterize patient-reported pain outcomes over time.

Analysis approach: Patients' ratings of dentin sensitivity will be compared across the observation times using generalized linear models. Terms representing individual practitioners and patients will be included as random effects in the analytic model, to account for correlation among multiple patients per practitioner and multiple observation times per patient. Terms representing observation time and treatment modality will be included as fixed effects. The statistical test that will be of primary interest will be the time by treatment interaction term, which would reflect different trajectories of reported pain levels among the treatment modalities. This analysis model will also provide group-specific means and standard errors, accounting for clustering, which will allow estimation of trajectories of pain outcomes across time. Plots of adjusted means across time will be constructed for each of the subgroups in the analysis, along with appropriate measures of variability. It should be noted that the measures of change within individual treatment groups do not separate change due to treatment from that due to natural time course or other causes. Comparisons of means between treatment groups do reflect the differences between treatment effects because the effects of causes that are common to both groups are removed in the calculation of the differences.

Depending on the nature of the distribution of the reported VAS scores, this analysis will be implemented either as a general linear mixed-model, if the residual distribution is approximately normal, or a generalized mixed-model, if a non-normal distribution is required. Other approaches that may be considered for the analysis of non-normal measures include using data transformations or analysis of ranked data.

Analysis plan for Secondary Objectives:

#1. To explore patient-, practice- and tooth- level characteristics that may contribute to practitioners' selected treatment(s) and approach(es) to care.

Analysis approach: Occurrence of patient-reported symptoms, predisposing factors and other patient-level variables, and practitioner-reported restoration-level and practice-level variables will be compared among the treatment modalities using a mixed-model multiple logistic regression approach. A term representing the individual practitioner will be specified as a random effect in the analytic model, and GEE estimation will be utilized in order to account for the clustering effect of multiple patients for each practitioner. Analyses will be conducted using each of the treatment modalities as the dependent variable. Potential predictor variables will be evaluated for association with the use of each treatment modality.

#2. To characterize patients' satisfaction with the received treatment of DH.

Analysis approach: Patients' reported satisfaction scores will be compared among the treatment modalities using mixed-model analysis of variance (ANOVA), accounting for correlated observations within practitioner. The specific implementation of the mixed-model ANOVA, as a normal-theory general linear model or a generalized linear model for non-normal data, will be based on the sample distribution of the scale scores. The statistical test that will be of primary interest will be the test for a main effect of treatment modality. Multiple comparisons will be conducted using Tukey's adjustment for multiple comparisons.

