3.2 Study Outcome Measures

3.2.1 Primary Outcomes

To characterize diagnosis and treatment of DH in the practice setting, practitioners' preferred methods of diagnosing and treating DH will be ascertained via a practitioner

online questionnaire to be completed upon study enrollment and via practitioner data collection forms during patient visits.

Diagnosis of dentin hypersensitivity:

Online practitioner questionnaire: Practitioners' preferred diagnostic procedures that are usually implemented when diagnosing DH in the practice setting will be ascertained. These will include: spontaneous patient report, patient report after dentist's query, applying air blast, applying cold water, scratching dentin with dental explorer, requesting numeric descriptor of pain, requesting visual scale descriptor of pain, and using an electric pulp tester.

Treatment modalities:

Online practitioner questionnaire: Practitioners' preferred method of treatment of DH and the rationale for the elected treatment or treatments will be ascertained. Questions will include preferred treatment modalities (see below) and approach(es) to treatment of DH (i.e., providing multiple treatments at one time, one treatment or staged approach, no treatment, and/or no advice).

Patient visit(s): The usual and customary treatment(s) for DH utilized by the participating practitioner will be applied or prescribed and recorded.

The following groups of treatment modalities will be ascertained:

1. Fluoride products (gels, varnishes, pastes, rinses)
2. Desensitizing over the counter (OTC) Potassium nitrate toothpastes
3. Glutaraldehyde/HEMA products
4. Bonding agents
5. Sealants
6. Restorative treatments
7. Lasers
8. Oxalates
9. No treatment
10. Advice
11. Other

Patient-reported pain outcomes:

Patient visit(s) and follow-up: Patient-reported pain outcomes will be assessed by changes in patient report of pain intensity, duration, and frequency. Patients' perception of pain will be assessed by the Visual Analog Scale (VAS) at baseline, 1 week-, 4 weeks- and 8 weeks- post-baseline. Duration, intensity, tolerability and pain description changes will be assessed by means of the Labeled Magnitude (LM) scales at baseline, 1 week-, 4 weeks- and 8 weeks- post-baseline (Heaton et al., 2013). If patients return

for a second- or third-line of treatment, these pain assessments will be implemented also at 1, 4 and 8 weeks after the initiation of the second- or third-line of treatment.

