4 STUDY DESIGN

- This is a prospective, multicenter cohort study of DH. For the study, practitioners and patients will be recruited from six National Dental PBRN regions across the US.
- The study population will consist of adult dental patients (19 years old or older) who have DH and the practitioners who provide treatment for DH. Dental practitioners are included in the population being studied because diagnostic modalities as well as treatment recommendations and approaches for DH are being studied. It is anticipated that approximately 180 dentist practitioners across the US will be enrolled (approximately 30 practitioners per National Dental PBRN region). Each dental practitioner will enroll approximately 14 study patients with an enrollment aim of 2,520 adult patients.
- The prospective, observational, multicenter design of the study will allow us to construct a picture of how patients with DH are cared for in dental offices across the US and how practitioner-, practice-, patient- and tooth- characteristics relate to the selected treatment(s) and approach(es) to care. The proposed study will provide further understanding about DH management based on a sample of US dental providers enrolled in the network and may provide data to establish guidelines for treating DH. The usual and customary treatment of DH that dentists apply in their practice will be assessed.
- After enrolling in the study and providing consent, practitioners will receive a link to a secure webpage and will be asked to complete an online questionnaire before recruiting and enrolling patients to the study.
- To determine if a patient meets the criteria for study inclusion, the patient must first indicate intraoral pain/sensitivity by self-report. Patients with a medical condition that could interfere with reliable pain reporting (e.g., cognitive impairment, dementia), chronic pain condition (fibromyalgia, lower back pain, irritable bowel syndrome, temporo-mandibular joint (TMJ) disorder), and patients who report having taken analgesics more than three times in the past week will be excluded from the study. Next, the practitioner will perform an oral examination to assess other causes of tooth sensitivity such as pulpitis or dental infection. A diagnosis of DH will be made when the practitioner has excluded other etiologies of odontogenic pain.

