11 STATISTICAL CONSIDERATIONS

The study is characterized by an estimation- rather than hypothesis-driven approach. The aims of identification and quantification of dentists' selected treatment(s) for DH and methods selected for the diagnosis of DH in the practice setting will be addressed by estimation of percentages of dentists using each method and percentages of patients for which each method was used, and calculation of confidence intervals (CIs) to evaluate the precision of each estimate.

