The outcome measures that were used for sample size calculations for tabulation of treatment and diagnostic method use were the treatment techniques listed by the dentists and the diagnostic techniques, as presented in the dentist surveys. The sample size calculations for these are identical, but the number of treatment techniques is not known in advance, while we will know the number of diagnostic techniques that will be included. Patients' rating of DH using VAS responses were used as the outcome variable for evaluation of patient-reported pain outcomes over time.

Test statistic

Power for hypothesis testing was based on t tests and chi-square tests. Precision of estimation of percentages was based on widths of 95% confidence intervals for the binomial distribution. Precision of estimation of mean change in pain scores was based on widths of 95% confidence intervals for the normal distribution.

For the primary objective, study precision calculations were based on widths of 95% confidence intervals, rather than on power of hypothesis tests.

Type I error rate

The Type I error rate will be set at 5% for all analyses.

Type II error rate

The target Type II error rate is 20%, corresponding to statistical power equal to 80%. Power was calculated for a range of effect sizes, yielding ranges of power estimates.

Method for adjusting calculations for planned interim analyses, if any

No interim analyses are planned.

Assumptions used in calculations

[figure not shown]
Confidence interval width and power estimation for percentages of the dichotomous outcomes use of treatment modality and use of diagnostic techniques were based on

event rates of 50%, yielding the most conservative estimates by providing the widest estimated confidence interval width and a lower bound on power. This approach was used in order to somewhat offset possible inflation of power estimates due to approximation of equivalence of adjusted chi-square and t tests to the proposed GEE analysis, or to other errors of assumption in the calculations.

[figure not shown]
Data for objectives 1 and 2 are collected cross-sectionally, at a single patient visit. Thus, withdrawals are not anticipated for these analyses. For objective 3, loss to follow-up is a possibility. All available data for each patient will be used in the GEE analysis models. Least-squares adjusted means will be calculated in order to avoid biasing main effects means due to missing values.

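### Primary Objective 1: the protocol states a patient-level percentage for each diagnostic method, but Section 11.2 analyses only practitioners' questionnaire answers, and the stated precision does not apply to those

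*Protocol*

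**What the plan says.** Some places in the protocol point to patient-level data on diagnosis:

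- Section 11 covers the treatment and diagnosis aims in one sentence and says that both will be addressed by "percentages of dentists using each method and percentages of patients for which each method was used".
- The opening of Section 3.2.1, again covering diagnosis and treatment together, names the online questionnaire and adds that information will be obtained "via practitioner data collection forms during patient visits".
- Section 11.1, on withdrawals, states: "Data for objectives 1 and 2 are collected cross-sectionally, at a single patient visit".

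Other places point to the questionnaire alone:

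- Section 11.2, Objective #1: "This will done by asking questions by means of an online questionnaire on what practitioners usually do when diagnosing DH". The analysis follows suit: "Practitioners' responses to questionnaire items will be summarized and reported as frequencies and percentages", with 95% confidence intervals.
- The diagnosis paragraph of Section 3.2.1 lists only the online questionnaire. The treatment paragraph beside it has a further entry for patient visits.
- Section 11.1 takes the sizing outcome for diagnosis from "the diagnostic techniques, as presented in the dentist surveys".
- Sections 4 and 7.2 place the questionnaire before any study patient is enrolled.

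Objective #2 in Section 11.2 has both practitioner and patient percentages, the latter adjusted for clustering by dentist. Objective #1 has no patient percentage.

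**The concern.** What a dentist reports usually doing and what was done for a given patient are different quantities. The first has the practitioner as its unit; the second has the patient, clustered within dentist. Section 11 states both for diagnosis, and Section 11.2 delivers only the first.

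This is more than a detail left to a statistical analysis plan, because Section 11.2 positively fixes both the data source and the unit. A plan that followed it would drop an estimate stated in Section 11. A plan that followed Section 11 would depart from Section 11.2.

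The same gap affects precision. Section 11.1 gives interval widths for the primary estimation aims as a whole, computed from patient numbers. A reader would take them to cover all percentages reported under the primary objectives, including those for diagnosis.

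**Working it through.** **Inputs.** From Section 11.1: 180 dentists; 14 patients each, so 180 × 14 = 2,520; a planning grid of 10 to 20 patients per dentist and intracluster correlation (ICC) 0.00 to 0.05; proportion 0.50; 95% confidence. From Section 11.2: Objective 1 summarises practitioners' responses, taken here as one per practitioner.

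**Formulas.** With m patients per dentist, the effective sample size is n_eff = 180m / [1 + (m − 1) × ICC]. The full interval width is 2 × 1.96 × √(0.25 / n_eff).

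**Step 1: the protocol's own range, 3.3% to 5.0%.**

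- m = 20, ICC = 0: n_eff = 3,600, width 3.27 points. This agrees with 3.3%.
- m = 10, ICC = 0.05: n_eff = 1,800 / 1.45 = 1,241, width 5.56 points. The stated 5.0% is not reproduced. A width of 5.02 points results from m = 10 with ICC 0.02, or from m = 14 with ICC 0.05. This is a separate discrepancy and does not alter the present point. On either figure, the range rests on more than a thousand effective patients.

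**Step 2: Objective 1 as Section 11.2 describes it.** n = 180, so the width is 2 × 1.96 × √(0.25 / 180) = 14.6 points, or ±7.3.

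**Step 3: the patient-level percentage in Section 11, at the chosen m = 14.**

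| ICC | n_eff | Width (points) |
|---|---|---|
| 0 | 2,520 | 3.9 |
| 0.02 | 2,520 / 1.26 = 2,000 | 4.4 |
| 0.05 | 2,520 / 1.65 = 1,527 | 5.0 |

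The interval for the analysis actually described is 14.6 / 5.0 = 2.9 to 14.6 / 3.9 = 3.7 times as wide.

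**Step 4: sensitivity to ICC.** A dentist's diagnostic habits may cluster more strongly than 0.05. The protocol gives no figure for this, so these values are assumptions: ICC 0.10 gives 5.9 points, 0.30 gives 8.6, and 0.50 gives 10.7. At ICC 1 the patient-level width equals the practitioner-level 14.6. The advantage shrinks as clustering rises.

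**Step 5: what a patient-level table could show.** Under Section 4, "the patient must first indicate intraoral pain/sensitivity by self-report", and Section 5.1 makes self-reported tooth pain part of the study's diagnosis. Spontaneous and prompted report combined would therefore be 2,520 / 2,520 = 100% of enrolled patients, whatever the practice. The split between the two is not fixed. Section 7.2 also has every patient complete a VAS at baseline, so a record that a visual scale was used could reflect the study rather than the dentist.

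**The case against.** The strongest reply is that the intended source can be recovered. Every passage specific to diagnosis names the questionnaire: the diagnosis paragraph of Section 3.2.1, Section 7.2, the sizing outcome in Section 11.1, and Section 11.2. The patient-level wording sits in sentences that treat diagnosis and treatment together, or in one whose purpose is to say that withdrawals are not expected. A questionnaire completed before enrolment also has a merit: the study's own VAS cannot contaminate it. This stands, and it makes a wording repair acceptable. It does not remove the conflict, because Section 11 names diagnosis explicitly, and the stated widths still do not describe 180 responses.

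Three stronger readings are tempting, and the protocol does not support them:

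- **That the entry rule predetermines the Objective 1 result.** It does not bias the analysis now planned. The questionnaire precedes enrolment and asks about usual practice. The rule matters only if a patient-level table is added.
- **That about 2,520 chairside observations of diagnostic method are promised and then discarded.** The wording is too loose for that. The case report forms are not shown, so it is unknown whether diagnostic method is recorded per patient.
- **That the questionnaire merely repeats an earlier survey.** The survey of 209 dentists in Section 2.1 covered one regional network in 2008 to 2009. This study covers six US regions.

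**Conclusion.** The point holds as an inconsistency in the estimand, and in the precision claimed for it, for one part of the primary objective. Section 11 states a patient-level percentage for diagnosis that Section 11.2 does not deliver. The precision that applies to Section 11.2 is about 14.6 points at a proportion of 0.50, against 3.9 to 5.0 points for 2,520 patients over the protocol's ICC range.

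These figures assume that all 180 practitioners respond once each, exactly 14 patients per dentist, and the Normal approximation that the protocol itself uses. The aim is descriptive, so no power or type I error figure is affected. Nor is the questionnaire analysis invalid: it estimates reported usual practice, and should be labelled and sized as that.

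**What to change.** **Preferred.** Record the diagnostic methods used for each patient on the existing Baseline Exam form, or use them if they are already recorded there. Add to Section 11.2, Objective #1, the percentage of patients per method, with the clustering adjustment already planned for Objective #2. Show it beside the questionnaire percentage, labelled as reported usual practice. Add two notes to the table: patient report, spontaneous or prompted combined, is fixed by eligibility; and the visual scale item excludes the VAS that the study itself requires.

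**Minimum.** Restrict the diagnosis wording in Sections 3.2.1, 11 and 11.1 to the percentage of practitioners reporting usual use of each method, and state the expected interval width for 180 responses.

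**Cost.** The minimum is a text edit. The preferred change needs a paragraph in the analysis plan and one table. If the form does not already hold the information, it also needs a new item and some recording time in the practice. That part cannot be costed, because the forms are not shown. It has to be settled before data collection, since methods not recorded at the visit cannot be reliably recovered later.

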Sample size requirements for the primary objective of characterizing the trajectories of patient-reported pain outcomes over the study period, and for comparing these changes among the different treatments selected by the practitioners, were based on the expected widths of 95% CIs for the percentages of use of each of the treatments and diagnostic methods, and secondarily on t tests for comparisons of changes in VAS scores between two treatments, adjusted for the effect of clustering and for multiple treatment comparisons, again in order to approximate the power of the proposed GEE analysis. Power was calculated for comparison of two groups because the actual number of treatments observed will not be known until after the data is collected. In the absence of information on group size, the sample was assumed to be equally divided. Power was calculated for the conventional "medium effect size", represented by a between-group difference in means equal to one-half of the within-group standard deviation. Additionally, the difference in means that would be detectable with 80% power was calculated, and expressed as a multiple of the within-group standard deviation. Expected CI widths were based on the Normal approximation to the binomial distribution, and were calculated around 50% in order to provide conservative estimation. Precision of estimation of mean change in pain scores was calculated based on the widths of 95% CIs for change in reported pain scores, also using the expected mean numbers of subjects in equal-sized treatment groups. These CIs are expressed in standard deviation units.

The actual analysis will compare all the treatment groups that occur in the study, using an analysis of variance approach which will incorporate the entire sample. While the groups will be smaller than in this approximation, this will be somewhat offset by incorporating the entire sample in calculation of the standard error, so that power will be greater than would be calculated using only a portion of the patients in separate pairwise comparisons of treatment groups.

The nQuery Advisor version 7.0 software package was used to calculate expected confidence interval widths and power estimates.

Outcome measure used for calculations

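### The pain model, followed literally as a random intercept per patient, assumes one variance and one correlation across four unlike ratings; the protocol also calls it GEE without stating robust errors, so the size of the primary-interest test is not secured

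*Protocol*

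**What the plan says.** Section 11.2, Primary Objective 3, sets out the model for the pain ratings: "Terms representing individual practitioners and patients will be included as random effects in the analytic model, to account for correlation among multiple patients". The sentence goes on to give the same terms the job of handling several observation times per patient. For the fixed part, "Terms representing observation time and treatment modality will be included as fixed effects". On inference, "The statistical test that will be of primary interest will be the time by treatment interaction term", and "This analysis model will also provide group-specific means and standard errors, accounting for clustering". On the model family, "this analysis will be implemented either as a general linear mixed-model, if the residual distribution is approximately normal, or a generalized mixed-model" if normality fails; transformation or ranks are also allowed.

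Section 11.1 describes the Objective 3 analysis differently. The VAS power calculation was adjusted "again in order to approximate the power of the proposed GEE analysis", and under loss to follow-up for Objective 3, "All available data for each patient will be used in the GEE analysis models".

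The rating times are in section 3.2.1: "Patients' perception of pain will be assessed by the Visual Analog Scale (VAS) at baseline, 1 week-, 4 weeks- and 8 weeks- post-baseline". Section 4 places the baseline rating in the dental office and the three follow-ups online or by mail. Section 11.1 sets the Type I error rate at 5% for all analyses.

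**The concern.** One random intercept per patient with independent residuals gives compound symmetry: the same variance at all four times, and the same correlation between baseline and week 8 as between week 4 and week 8. The design makes that doubtful. The ratings are unequally spaced, the first is taken in a different setting from the rest, and treatment falls between it and the others.

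If the true covariance departs from compound symmetry, the pooled residual variance is an average that fits no particular change exactly. The time-by-treatment test and the standard errors of change then do not have their nominal properties. This arises even with no clustering by dentist, so the practitioner term does not repair it. GEE with robust errors would, but section 11.2 specifies random effects for this objective, and neither section mentions robust errors.

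**Working it through.** **The plan's own figures.** Section 11.1 gives detectable differences of 0.095 SD (20 patients per dentist, ICC 0) and 0.160 SD (10 per dentist, ICC 0.05). With Neff = 180m/(1 + (m − 1)ICC) and d = (1.960 + 0.842)√(4/Neff), two-sided with two equal groups:
- m = 20, ICC 0: Neff = 3,600, d = 0.0934.
- m = 10, ICC 0.05: Neff = 1,800/1.45 = 1,241.4, d = 0.1590.

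Both agree with the protocol to within 2%. They are in SD units for a single outcome, so they do not involve the within-patient covariance and cannot settle this point.

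**Inputs for the check.** From the protocol: four ratings, nominal 5%, and four equal groups (section 11.1's precision assumption). Assumed, because the protocol gives none: the correlations and SDs. Also assumed: complete data, no dentist clustering, two-sided tests.

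**Step 1, fitted residual variance.** Under a random intercept, the expected residual variance is the mean of the four variances minus the mean of the six covariances. Take all SDs equal to 1, baseline-to-follow-up correlation 0.3 (three pairs) and follow-up-to-follow-up correlation 0.7 (three pairs): 1 − (3 × 0.3 + 3 × 0.7)/6 = 0.50.

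**Step 2, change contrasts.** The model takes the variance of any change to be 2 × 0.50 = 1.00.
- Baseline to week 8: true variance 2 − 2 × 0.3 = 1.40. Ratio of model to true SE = √(1.00/1.40) = 0.845. Size = 2{1 − Φ(1.96 × 0.845)} = 9.8%.
- Week 4 to week 8: true variance 2 − 2 × 0.7 = 0.60. Ratio 1.291. Size = 1.1%.

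**Step 3, interaction test.** With G groups, the large-sample statistic is a weighted sum of three independent chi-squares on G − 1 df. The weights are the eigenvalues of the within-patient contrast covariance divided by their mean. It is referred to chi-square on 3(G − 1) df. At 0.3/0.7 the weights are 0.6, 0.6 and 1.8. With four groups the size is 7.0%; with two groups it is 6.3%.

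**Step 4, other covariances (four groups).** The paired correlations are baseline-to-follow-up / among follow-ups. Contrast size is for baseline to week 8.

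| Assumed covariance | SE ratio, change from baseline at weeks 1 / 4 / 8 | Contrast size | Interaction size |
|---|---|---|---|
| Compound symmetry, 0.5 | 1.00 / 1.00 / 1.00 | 5.0% | 5.0% |
| 0.4 / 0.6, equal SD | 0.91 at all three | 7.4% | 5.6% |
| 0.3 / 0.7, equal SD | 0.85 at all three | 9.8% | 7.0% |
| 0.3 / 0.7, baseline SD 1.2 | 0.82 at all three | 10.7% | 7.8% |
| 0.2 / 0.7, baseline SD 1.2 | 0.81 at all three | 11.3% | 8.2% |
| AR(1) by visit, 0.6 | 1.17 / 0.92 / 0.83 | 10.3% | 6.5% |
| AR(1) by week, 0.9 | 1.89 / 1.02 / 0.79 | 12.0% | 8.1% |
| 0.4 / 0.6, baseline SD 0.7 | 0.96 at all three | 5.9% | 5.1% |
| 0.5 / 0.6, baseline SD 0.7 | 1.00 at all three | 4.9% | 5.0% |
| 0.5 / 0.5, baseline SD 0.7 | 1.06 at all three | 3.7% | 5.2% |
| 0.6 / 0.4, equal SD | 1.12 at all three | 2.8% | 5.6% |

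**Step 5, plotted means.** The standard error of a group mean at one time uses the total variance, patient plus residual. At 0.3/0.7 with equal SDs the fit gives 0.50 + 0.50 = 1.00, which is the true variance. The ratio is 1.00 at all four times.

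**Step 6, robust errors.** In 2,000 simulated trials (180 dentists × 14 patients, four groups, ICC 0.05), the random-intercept test against the practitioner-clustered robust test gave 5.0% against 4.2% under compound symmetry, 7.5% against 5.5% at 0.3/0.7, and 5.5% against 4.6% under AR(1) by visit. The Monte Carlo error is about 0.5 points.

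**The case against.** The strongest reply is that the text does not say the random effect is an intercept, does not say it is the only within-patient structure, and names no residual covariance. A patient random effect can sit beside random slopes or a structured residual, and such detail commonly belongs in the statistical analysis plan, which is not at hand. Section 11.1 also calls the analysis GEE, whose usual robust errors do not need equal variances or correlations. And section 11 describes the study as driven by estimation rather than hypothesis tests.

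Much of this stands. The plan does not compel compound symmetry, and under the generalized-model option equal variances need not follow. What remains is that section 11.2 names the device for the repeated ratings, and that device read in the ordinary way carries the constraint. Section 11.1 names a different method without the feature that would remove it. That is a conflict in the stated text, not only a missing detail.

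Two stronger readings are tempting. A reader might infer that change-from-baseline errors are too small in a known direction. The documents give no covariance, and the table shows ratios above 1 at week 1 under AR(1), and at all three follow-ups in two of the cases with exchangeable follow-ups. A smaller baseline SD is also plausible, since everyone reports tooth pain at entry while follow-up mixes responders and non-responders. A reader might also infer that the error bars on the plotted trajectories are wrong. Those are bars on means, and step 5 shows they can be exactly right while the errors of change are not.

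**Conclusion.** The point holds in a conditional form. If section 11.2 is followed as a linear mixed model with patient intercepts and independent residuals, the test of primary interest keeps its 5% size only when the covariance is close to compound symmetry. For the pattern this design suggests (0.2 to 0.4 with baseline, 0.6 to 0.7 among follow-ups, baseline SD 1.0 to 1.2 times follow-up), its size is about 5.6% to 8.2%, and that of a baseline-to-week-8 contrast about 7% to 11%. The contrast is not one the protocol names, so the interaction figure is the one to weigh. Those ranges rest entirely on assumed covariances, complete data and four equal groups. Over all the covariances tried, the interaction size runs from about 5.0% to 8.2%. The effect is modest, but it falls on the test the protocol singles out and is nearly free to avoid.

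**What to change.** In section 11.2, Primary Objective 3, reconcile the random-effects wording with the GEE wording in section 11.1 so that one analysis is described. Then specify one of two options:

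- an unstructured within-patient covariance over baseline and weeks 1, 4 and 8 of a treatment line, keeping the practitioner term. This has 4 variances and 6 correlations, 10 parameters in all, which about 2,500 patients support easily; or
- practitioner-clustered robust standard errors, to be used in any case where a generalized model is needed, since the unstructured option does not carry over directly.

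Take the time-by-treatment test and the standard errors of change from that model. The phrase about a treatment line matters because patients who return for second- or third-line treatment restart the sequence of ratings (section 6.6), so four ratings do not describe every patient. The cost is a few sentences in the plan, with no added patients, visits or data.
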